6.2.3 Dose Modification of ¹⁸F-FFNP

No dose modification of ¹⁸F-FFNP is planned in this study.

6.3 Dietary Restrictions

None.

6.4 Monitoring Subject Compliance

Study drug will be administered or dispensed only to eligible subjects under the supervision of the investigator or identified sub-investigator(s). The appropriate study personnel will maintain records of study drug receipt and dispensing. Comprehensive instructions will be provided to the subject in order to ensure compliance with dosing procedures. The subject will be requested to maintain a medication diary of each dose of medication. The medication diary and all study drug containers will be returned to clinic staff at the end of each cycle.

6.5 Follow-Up Period

Subjects will be followed for one year after removal from the study treatment or until death, whichever occurs first.

7 ADVERSE EVENTS: DEFINITIONS, COLLECTION AND REPORTING REQUIREMENTS

7.1 Definitions

7.1.1 Adverse Event

Any untoward medical occurrence in a patient or clinical investigation subject administered a pharmaceutical product and which does not necessarily have to have a causal relationship with this treatment. (International Conference on Harmonization [ICH], E2A, E6).

This study will utilize the NCI Common Terminology Criteria for Adverse Events (CTCAE) version 5.0, located on the CTEP web site:

https://ctep.cancer.gov/protocolDevelopment/electronic_applications/ctc.htm

AEs may be spontaneously reported by the patient and/or in response to an open question from study personnel or revealed by observation, physical examination or other diagnostic procedures.

7.1.2 Serious Adverse Event (SAE)

Serious Adverse Event (SAE) means any untoward medical occurrence that results in any of the following outcomes:

- **Death.** Results in death.
- **Life threatening.** Is life threatening (refers to an AE in which the patient was at risk of death at the time of the event. It does not refer to an event which hypothetically might have caused death if it were more severe).
- **Hospitalization.** Requires inpatient hospitalization or prolongation of an existing hospitalization (see clarification in the paragraph below on planned hospitalizations).
- **Disability/incapacity.** Results in persistent or significant disability or incapacity. (Disability is defined as a substantial disruption of a person's ability to conduct normal life functions).
- **Pregnancy**
- **Medically important event.** This refers to an AE that may not result in death, be immediately life threatening, or require hospitalization, but may be considered serious when, based on appropriate medical judgment, may jeopardize the patient, require medical or surgical intervention to prevent one of the outcomes listed above, or involves suspected transmission via a medicinal product of an infectious agent. Examples of such medical events include allergic bronchospasm requiring intensive treatment in an emergency room or at home, blood dyscrasias or convulsions that do not result in inpatient hospitalization, or the development of drug dependency or drug abuse; any organism, virus, or infectious particle (e.g., prion protein transmitting transmissible spongiform encephalopathy), pathogenic or nonpathogenic, is considered an infectious agent.

7.1.3 Attribution of an Adverse Event

Attribution is an assessment of the relationship between the AE and the medical intervention.

Relationship Assessment: In-Depth Definitions

For all collected AEs, the clinician who examines and evaluates the subject will determine the adverse event's causality based on temporal relationship and his/her clinical judgment. The degree of certainty about causality will be graded using the categories below:

Definitely Related: There is clear evidence to suggest a causal relationship, and other possible contributing factors can be ruled out. The clinical event, including an abnormal laboratory test result, occurs in a plausible time relationship to drug administration and cannot be explained by concurrent disease or other drugs or chemicals. The response to withdrawal of the drug (de-

challenge) should be clinically plausible. The event must be pharmacologically or phenomenologically definitive, with use of a satisfactory re-challenge procedure if necessary.

Probably Related: There is evidence to suggest a causal relationship, and the influence of other factors is unlikely. The clinical event, including an abnormal laboratory test result, occurs within a reasonable time sequence to administration of the drug, is unlikely to be attributed to concurrent disease or other drugs or chemicals, and follows a clinically reasonable response on withdrawal (de-challenge). Re-challenge information is not required to fulfill this definition.

Possibly Related: There is some evidence to suggest a causal relationship (e.g., the event occurred within a reasonable time after administration of the trial medication). However, the influence of other factors may have contributed to the event (e.g., the subject's clinical condition, other concomitant events). Although an adverse drug event may rate only as "possibly related" soon after discovery, it can be flagged as requiring more information and later be upgraded to "probably related" or "definitely related", as appropriate.

Unlikely: A clinical event, including an abnormal laboratory test result, whose temporal relationship to drug administration makes a causal relationship improbable (e.g., the event did not occur within a reasonable time after administration of the trial medication) and in which other drugs or chemicals or underlying disease provides plausible explanations (e.g., the subject's clinical condition, other concomitant treatments).

Unrelated: The AE is completely independent of study drug administration, and/or evidence exists that the event is definitely related to another etiology. There must be an alternative, definitive etiology documented by the clinician.

7.1.4 Expectedness of an Adverse Event

Study investigator or treating physician will be responsible for determining whether an AE is expected or unexpected as indicated in the protocol, informed consent form and/or drug information brochure. An AE will be considered unexpected if the nature, severity, or frequency of the event is NOT consistent with the risk information previously described for the study intervention.

7.2 Collection and Reporting Requirements for Adverse Events and Serious Adverse Events

7.2.1 Collection of Adverse Events

All (or specify if only certain grade AE needed) adverse events (including SAEs) must be recorded in OnCore® and an adverse event log. All AEs required to be collected must be graded according to the CTCAE v5. When possible, signs and symptoms indicating a common underlying pathology should be noted as one comprehensive event. Investigator's or treating physician's assessment of AE attributions must also be documented.

AEs will be collected from the time the subject signs the consent form through 30 days following last dose of study drug(s). AEs will be tracked and followed until resolution, subject withdraws consent, or is lost to follow-up (including subjects who discontinue early). All adverse events collected per the protocol will be followed with appropriate medical management until they are resolved, if they are related to the study treatment, or until the investigator deems the event to be chronic.

Please see Table 7 to identify the adverse events that need to be reported.

7.2.2 Reporting of Adverse Events and Serious Adverse Events

All serious adverse events (SAEs) that occur after the subject has signed the consent form through 30 days following last dose of study drug(s) will be reported. All SAEs will be followed until satisfactory resolution, or until the investigator deems the event to be chronic.

All serious adverse events (SAEs) must also be documented in OnCore®.

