1.3.1 Clinical Pharmacokinetics of Fulvestrant

The recommended dose (intramuscular injection) is 500 mg at intervals of one month, with an additional 500 mg dose given two weeks after the initial dose. Fulvestrant is slowly absorbed, reaching maximum plasma concentrations after about five days. Steady state is achieved within the first month of dosing. At steady state there is more than a twofold difference between mean C_{max} and C_{min}. After intramuscular administration, the exposure is approximately dose proportional in the dose range of 50 to 500 mg.(39) Fulvestrant is subject to extensive and rapid distribution. Fulvestrant is eliminated mainly by metabolism. The major route of excretion is via the feces with less than 1% being excreted in the urine. Fulvestrant has a high clearance, suggesting that it is a drug with a high extraction ratio. The terminal half-life after intramuscular administration is governed by the absorption rate and was estimated to be 40 to 50 days. An *in vitro* inhibition study showed no relevant inhibition of CYP1A2, 2C9, 2C19, 2D6 or 3A4 by fulvestrant. The lack of inhibition of CYP3A4 was confirmed in an *in vivo* interaction study with midazolam. Studies using human liver preparations and recombinant human enzymes indicate that CYP3A4 is the only P450 isoenzyme involved in the oxidation of fulvestrant; however, non-P450 routes appear to be more predominant *in vivo* as interaction studies with rifampicin (CYP3A4 inducer) and ketoconazole (CYP3A4 inhibitor) demonstrated no effect on fulvestrant pharmacokinetics. The relative contribution of P-450 and non-P-450 routes *in vivo* is unknown.(39) The potential for interaction with fulvestrant therefore appears to be low. Increased exposure to fulvestrant was observed in patients with moderate hepatic impairment (Child-Pugh class B); therefore, a dose of 250 mg is recommended in these cases. Fulvestrant has not been administered to patients with severe hepatic impairment.(39)

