7.3 Expedited Reporting of Serious Adverse Events

Depending on the nature, severity, and attribution of the serious adverse event, an SAE report will be phoned in, submitted in writing, or both according to the table below. All serious adverse events must also be reported to the UWCCC Data and Safety Monitoring Committee Chair. All serious adverse events must also be reported to the UW IRB (if applicable), and any sponsor/funding agency not already included in the list.

Determine the reporting timeline for the SAE in question by using the following table. Then refer to sections 7.3.3 AMD 7.3.5 below if the SAE occurred at the UWCCC or sections 7.3.4 and 7.3.5 if the SAE occurred at 1 South Park, Johnson Creek, or a WON Site.

Phase 1 and Early Phase 2 Studies: Expedited Reporting Requirements for Adverse Events that Occur on Studies under an IND/IDE within 30 Days of the Last Administration of the Investigational Agent/Intervention ^{1,2}

TABLE 7:- FDA Reporting Requirements for Serious Adverse Events (21 CFR Part 312)

NOTE: Investigators **MUST** immediately report to the UWCCC and any other parties outlined in the protocol ANY serious adverse events, whether or not they are considered related to the investigational agent(s)/intervention (21 CFR 312.64).

An adverse event is considered serious if it results in ANY of the following outcomes:

- 1) Death.
- 2) A life-threatening adverse event.
- 3) An adverse event that results in inpatient hospitalization or prolongation of existing hospitalization for \geq 24 hours.
- 4) A persistent or significant incapacity or substantial disruption of the ability to conduct normal life functions.
- 5) A congenital anomaly/birth defect.
- 6) Important Medical Events (IMEs) that may not result in death, be life-threatening, or require hospitalization, may be considered serious when, based upon medical judgment, they may jeopardize the patient or subject and may require medical or surgical intervention to prevent one of the outcomes listed in this definition (FDA, 21 CFR 312.32; ICH E2A and ICH E6).

ALL SERIOUS adverse events that meet the above criteria **MUST** be immediately reported to the UWCCC within the time frames detailed in the table below:

Hospitalization	Grade 1 and Grade 2 Time Frames	Grade 3-5 Time Frames
Resulting in hospitalization \geq 24 hrs	10 Calendar Days	24 Hour; 5 Calendar Days
Not resulting in Hospitalization \geq 24 hrs	Not required	

Expedited AE reporting timelines are defined as:

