- **24-Hour; Five Calendar Days** – The AE must initially be reported within 24 hours of learning of the AE, followed by a complete expedited report within five calendar days of the initial 24-hour report.
- **10 Calendar Days** – A complete expedited report on the AE must be submitted within 10 calendar days of learning of the AE.

¹ Serious adverse events that occur more than 30 days after the last administration of investigational agent/intervention and have an attribution of possible, probable, or definite require reporting as follows:

Expedited 24-hour notification followed by complete report within five calendar days for:

- All grade 3, 4, and 5 AEs.

Expedited 10 calendar day reports for:

- Grade 2 AEs resulting in hospitalization or prolongation of hospitalization.

² For studies using PET or SPECT IND agents, the AE reporting period is limited to 10 radioactive half-lives, rounded UP to the nearest whole day, after the agent/intervention was last administered.

Footnote "1" above applies after this reporting period.

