7.5.1.4 Embryo-Fetal Toxicity

Fulvestrant can cause fetal harm when administered to pregnant women. Women who are not post-menopausal or surgically sterile must be treated with a GnRH agonist to be eligible to participate. Women must not donate eggs or become pregnant during participation or for 6 months

after stopping the drugs. Male breast cancer patients participating in the trial must not donate sperm or get their partners pregnant during treatment or within 6 months after their last dose. Subjects who have sexual intercourse which may result in pregnancy will be required to use contraception during study participation and for 6 months after their last dose.

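### Pregnancy is an SAE and must be avoided for 6 months after the last dose, but the reporting rules leave about 5 of those months without pregnancy reporting

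*Combined protocol and SAP*

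**What the plan says.** All references are to the combined protocol and SAP.

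- **7.1.2** lists pregnancy among the outcomes that make an event serious.
- **7.5.1.4** states that fulvestrant can harm a fetus. For women: "Women must not donate eggs or become pregnant during participation or for 6 months" after stopping the drugs. Men "must not donate sperm or get their partners pregnant during treatment or within 6 months after their last dose". Subjects whose intercourse could lead to pregnancy must use "contraception during study participation and for 6 months after their last dose".
- **7.2.1** collects AEs from consent to 30 days after the last dose. **7.2.2** sets the same limits for SAEs, which "through 30 days following last dose of study drug(s) will be reported".
- **7.3, Table 7** has its own seriousness list. It includes congenital anomaly or birth defect, which 7.1.2 does not, and omits pregnancy. It also attaches a 24-hour threshold to hospitalization. It says that "ALL SERIOUS adverse events that meet the above criteria" must be reported immediately, within the time frames of a grid by grade and hospitalization. In that grid, grade 1-2 events without a stay of at least 24 hours need no report.
- **Table 7, footnote 1** requires expedited reports for "Serious adverse events that occur more than 30 days after the last administration of investigational agent/intervention and have an attribution of possible, probable, or definite", but only for grade 3-5 events and for grade 2 events with hospitalization.
- **Study Calendar and 6.5**: follow-up runs every 3 months for a year, by telephone or chart review if preferred, and survival status is the only item listed. **5.3.2** requires no appointments beyond 30 days.

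**The concern.** The protocol names a fetal risk, sets the period over which pregnancy must be avoided, and calls the event serious. Its collection rules then stop about 5 months before that period ends. A site following the text exactly could learn of a pregnancy in the third month after the last dose and have no stated duty to report it or follow it to outcome. For the partner of a male subject there is no stated duty at any time, because 7.1.1 defines an adverse event as occurring in a patient or subject.

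The population at risk is not empty: premenopausal women on a GnRH analogue and men are both eligible (section 4.2). What is at stake is safety information on a small number of events, each of them serious.

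The grid adds a second difficulty, which applies inside the 30 days too. A grade 1-2 SAE without a 24-hour stay must be reported under 7.2.2 and need not be under Table 7.

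**Working it through.** The plan gives no figure on this point, so there is none to reproduce. The check is window arithmetic followed by a trace through the rules.

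**1. Share of the post-dose period not covered.** Inputs: 30 days (7.2.1, 7.2.2) and 6 months (7.5.1.4). Taking 6 months as 180 days is an assumption.

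- Covered: 30/180 = 16.7%.
- Not covered: (180 - 30)/180 = 150/180 = 83.3%.
- With 6 months as 184 days: 154/184 = 83.7%.
- If the safety visit takes place at its latest (30 + 14 = 44 days) and everything up to it is counted: (182.6 - 44)/182.6 = 75.9%.

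**2. Share of the whole avoidance period.** Section 7.5.1.4 also covers participation, and time on treatment is collected. With T days on treatment and 6 months as 182.6 days, the uncovered share is 152.6/(T + 182.6):

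| Time on treatment | Uncovered share |
|---|---|
| 8 weeks (56 days) | 152.6/238.6 = 64% |
| 16 weeks (112 days) | 152.6/294.6 = 52% |
| 24 weeks (168 days) | 152.6/350.6 = 44% |
| 1 year (365 days) | 152.6/547.6 = 28% |

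The share exceeds one half only if T is below 152.6/0.5 - 182.6, or about 123 days.

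**3. An uncomplicated pregnancy found in month 3 after the last dose, traced through each rule.**

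- 7.2.1 and 7.2.2: outside the 30 days, so not collected or reported.
- Table 7 seriousness list: pregnancy is absent. Birth defect is present, but it is known only at or near the outcome, and nothing prompts anyone to look for it if the pregnancy was never notified.
- Footnote 1: needs attribution to drug and a qualifying grade. A pregnancy without complications would not normally meet this.
- Follow-up contacts: survival status only. The calendar places pregnancy tests at screening and cycle 1 day 1 only.
- If the pregnancy is in a male subject's partner, no rule applies in any month.

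**4. Grade 1-2 SAEs within 30 days.** Section 7.2.2 reports all SAEs, and the note to Table 7 has investigators report any SAE immediately. The grid, introduced as the timetable for all serious events, exempts grade 1-2 events without a 24-hour stay. The three statements cannot all be followed as written.

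**The case against.** The strongest reply is that the safety net is wider than the 30-day rule. Several parts of it stand.

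- A reader might infer that SAE reporting closes altogether at day 30. It does not: footnote 1 has no end date, and a serious, drug-attributed complication of a pregnancy could qualify. The pregnancy itself would not normally do so.
- A reader might infer that most of the risk period is uncollected. That is true of the 6 months after the last dose. For the full period including treatment it depends on treatment duration, as step 2 shows.
- A reader might infer that low-grade SAEs are lost. Section 7.3 concerns expedited reporting, so the grid cell can be read as setting no expedited clock. Meanwhile 7.2.2 still requires every SAE to be documented in OnCore, and 11.6 has the DSMC chair review all of them. The wording conflicts, but loss of data is not shown.
- A chart review at a follow-up contact might reveal a pregnancy, and 5.3 keeps discontinued subjects under AE and SAE reporting. But that reporting is according to the protocol, which brings back the 30-day limit.
- SAE handling is partly delegated to SOPs and IRB guidelines that are not part of the document. It cannot therefore be claimed that the IND file would be silent.
- The fulvestrant half-life, which "was estimated to be 40 to 50 days", might tempt a reader to compute the drug remaining at day 30. Section 1.3.1 says this half-life is governed by absorption, and the document does not tie it to fetal risk. The point does not need it.
- With GnRH analogues, pregnancy testing and contraception required, the expected count is very low. This limits the weight of the point but does not remove the mismatch.

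**Conclusion.** The point holds as an internal inconsistency in safety reporting. Sections 7.1.2, 7.2.1, 7.2.2, 7.3 (Table 7 and footnote 1) and 7.5.1.4 do not agree on whether, and for how long, a pregnancy is reported. About 150 of 180 post-dose days (83%; 76% if a day-44 safety visit is counted) carry no stated duty to report one, and partner pregnancy has no provision at any time. The grade 1-2 cell of Table 7 is a separate conflict of wording with 7.2.2.

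The size rests on taking 6 months as 180 to 184 days and on the protocol text alone, since SOPs could add requirements. The document does not support the wider claims that all SAE reporting ends at 30 days or that low-grade SAEs go unrecorded. The matter should be corrected, but it does not touch the ORR estimate, the two-stage rule or its error rates.

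**What to change.** 1. **7.2.2**: state that any pregnancy in a subject, or in the partner of a male subject (with the partner's consent), is reported from consent to the end of the protocol's own 6-month post-dose period, whatever its grade or attribution, and followed to outcome. Starting at consent matches 7.2.2 and covers the optional baseline PET scan before cycle 1 day 1. Outcome follow-up should be allowed to outlast the one year in 6.5: assuming about 9 months' gestation, a conception at the end of month 6 leads to a birth near month 15.
2. **Table 7**: add a pregnancy line with its own time frame.
3. **Follow-up CRF**: at the existing 3- and 6-month contacts, ask about any pregnancy (subject or partner) and any serious event considered related. The contacts are timed from the end-of-treatment visit with a 14-day window either way, so repeating the pregnancy question at the 9-month contact would catch late conceptions.
4. **SAE definition**: use one list in 7.1.2 and Table 7, containing both pregnancy and congenital anomaly or birth defect, with one hospitalization definition.
5. **Grid**: reconcile the grade 1-2 cell with 7.2.2, either by giving it a time frame or by saying that it waives only the expedited report.

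The cost is protocol and CRF wording, a few extra reports and a partner-consent step. No new visits are needed.

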7.2.2.1 Reporting Instructions — Serious Adverse Events — Reported within 24 Hours

Serious adverse events requiring reporting within 24 hours (as described in the protocol) must also be reported to the Data and Safety Monitoring Committee (DSMC) chair via an email to [contact] within one business day. The OnCore® SAE Details Report must be submitted along with other report materials as appropriate (NCI AERs form or FDA Medwatch Form no. 3500 and/or any other documentation available at that time of initial reporting). The DSMC chair will review the information and determine if immediate action is required.

Within 10 working days, all available subsequent SAE documentation must be submitted electronically along with a 24-hour follow-up SAE Details Report and a completed UWCCC SAE Routing Form to [contact]. All information is entered and tracked in the UWCCC database.

The principal investigator notifies all investigators involved with the study at the UWCCC, the IRB, the sponsor, and the funding agency and provides documentation of these notifications to the DSMC. If the SAE occurs on a clinical trial in which the UW PI serves as the sponsor investigator, the PI reviews the event to determine whether the SAE requires reporting to the FDA and other participating investigators. For a multiple institutional clinical trial, the PI is responsible for ensuring that SAEs are reported to the sponsor as well as to all participating investigators. See Section 7.3 for detailed instructions on SAE reporting.

